[figure not shown]
*p values are relative to each population's Baseline.

A subpopulation of STEADFAST participants with probable Alzheimer's disease and type 2 diabetes was evaluated during post hoc, exploratory, subgroup analyses of the STEADFAST Study. Patients with type 2 diabetes were selected because they are known to have increased levels of AGEs; and increased levels of AGEs are known to induce RAGE expression. Therefore, HbA1c was chosen as a surrogate for identifying individuals with elevated levels of AGEs and high RAGE expression. Based on the hypothesis that subjects with presumed increased expression of RAGE would demonstrate enhanced effects from a RAGE antagonist, the subgroup was defined as those STEADFAST participants with Baseline HbA1c $\geq 6.5\%$. The objective of the subgroup analysis was to determine if a differential response to azeliragon was observed in patients with increased HbA1c.

Twenty-four subjects (17 azeliragon and 7 placebo) in the STEADFAST A-study dataset were identified as the Target Analysis Set (TAS). The TAS represents the intended subject population for future studies and is defined as subjects with HbA1c $\geq 6.5\%$ at Baseline and evidence of cognitive impairment at Baseline (ADAS-cog ≥ 10). Twenty-six subjects (13 azeliragon and 13 placebo) in the STEADFAST B-

study were identified as the TAS with Baseline HbA1c \geq 6.5% and ADAS-cog \geq 10. Unfortunately, the B-study was terminated by the sponsor and limited data are available beyond Month 9 for this subgroup. [Figure 2](#) displays the Change from Baseline in ADAS-cog₁₁ for the A-Study and B-Study in the TAS.

Figure 2. Change from Baseline in ADAS-cog: Type 2 Diabetic Subgroup (TTP488-301 [Target Analysis Set])

Results from the A-Study that completed the 18-month treatment period as planned, show a clear delineation between azeliragon and placebo groups in ADAS-cog throughout the duration of the study; separation achieves nominal statistical significance at multiple timepoints throughout treatment. The azeliragon-treated group (n=17) demonstrated a 3.8-point benefit on ADAS-cog relative to the placebo group (n=7) at Month 6, which was nominally statistically significant ($p = 0.009$). The azeliragon-treated group went on to demonstrate a 6.1-point benefit on ADAS-cog relative to the placebo group at Month 18, which was nominally statistically significant ($p = 0.018$).

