Results from the B-Study that terminated after approximately 12 months of treatment, show numerical values on ADAS-cog change from baseline favoring azeliragon. The azeliragon-treated group (n=13) demonstrated a 1.9-point benefit on ADAS-cog relative to the placebo group (n=13) at Month 6. The azeliragon-treated group went on to demonstrate a 3.6-point benefit on ADAS-cog relative to the placebo group at Month 12.

Change from Baseline in CDR-sb was evaluated for the A-Study and B-Study in the TAS. Results from the A-Study that completed the 18-month treatment period as planned, show a clear delineation between azeliragon and placebo groups in

CDR-sb. The azeliragon-treated group (n=17) demonstrated a 1.7-point benefit on CDR-sb relative to the placebo group (n=7) at Month 18 (p = 0.05).

[figure not shown]
CDR-sb results from the B-Study are difficult to interpret. The planned study duration of 18 months was intended to allow sufficient time to see decline in the functional measure. Unfortunately, the B-study was terminated prematurely by the sponsor and limited data are available beyond Month 6 for the B Study type 2 diabetic subgroup. In the B-Study at Month 12, the azeliragon-treated group (n=13) demonstrated a 1.5-point change from Baseline while the placebo-treated group (n=13) had a 0.8-point change from Baseline. The inherent variability of the CDR-sb measure combined with the small sample size and shorter study duration for subjects in the B study has limited the interpretation of the functional endpoint in the B-Study.

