1.6 Sample Size and Power Considerations

Original Sample size considerations for Part 1 (from protocol):

Assuming a standard deviation of the change from Baseline to Month 6 in ADAS-cog14 of 4, using $\alpha = 0.05$, a total sample size of approximately 82 subjects in balanced allocation (41 subjects per group) provides at least 90% power to detect a difference between treatment groups of 2.9 using a 2-sided, 2-sample t-test. Assuming a dropout rate of 18% or less, randomization of 100 subjects provides adequate statistical power for Part 1 to demonstrate superiority of azeliragon over placebo based on the ADAS-cog14. (Section 9.2).

Recalculated power considerations for Part 1:

ADAS-Cog: Estimates and standard deviations were drawn from a model that fit change in ADAS-Cog11 over time using the data from the STEADFAST A-study and B-study combined (N=880). The model utilized all individuals in the study. Estimates were drawn at an HbA1C of 7.2 (average from present TTP488-305 study; Part 1). The estimates of standard deviation and effect size for the change from baseline in ADAS-Cog was 3.4 and -1.54 respectively. Given a sample size of 43, a two-sided α of 0.05 would result in 30% power to detect a significant effect. If we observe the estimated effect size and standard deviation at the given sample size in Part 1 of the current study (TTP-305) we would expect to observe a p-value of 0.144 which could be considered evidence of a trend.

Previous studies (Siemers et al 2016) suggest that mean to standard deviation ratio between ADAS-Cog 11 and 14 are similar, therefore it is expected that the estimates drawn using ADAS-Cog11 will be applicable to ADAS-Cog14 data.

Cognitive Composite: The association of treatment was also tested using a composite that was derived from STEADFAST A and B studies. Composites allow the global assessment of multiple aspects of disease as well as exclusion of items that do not contribute to progression and thus add noise to the data. The composite is composed of the ADAS-Cog comprehension, word finding difficulty, and remembering test instructions variables. The composite will be calculated by summing the within visit z-scores for each item across individuals. Z-scores are calculated by subtracting the individual item score at visit x from the baseline mean item score and dividing this value by the item standard deviation at baseline.

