The ADAS-Cog variables included in the model were chosen using PLS regression where treatment status at 6 months was the outcome variable and ADAS-Cog 11 and CDR-SB individual items were predictor variables. The PLS was modeled using

STEADFAST study B as this dataset showed a smaller ADAS-Cog effect with treatment.

PLS estimates and standard deviations were drawn from the STEADFAST data (A-study and B-study combined) as above for ADAS-cog. The model fit change in PLS over time with estimates drawn at an HbA1C of 7.2. The estimates of standard deviation and effect size for the change from baseline were -0.92 and 1.5, respectively. Given a sample size of 43, an alpha of 0.05 would result in 49% power to detect a significant effect. If we observe the estimated effect size and sd at the given sample size in the present study (Part 1) we would expect to observe a p-value of 0.052 indicating that the composite is somewhat more sensitive to treatment effects than the ADAS-cog 11.

Modified Cognitive Composite: The STEADFAST analysis indicates that a portion of the observed change may be due to age-related cognitive decline. To assess this, a modified composite that incorporated aspects associated with cognitive decline due to aging, specifically trail making test (TMT A/B) and Controlled Oral Word Association Test (COWAT) was generated. As these variables are not available in ELEVAAGE, historic data (ADNI) was used to identify the best surrogate for each. All surrogates were found to be within ADAS-Cog individual items. Word finding difficulty was found to be a suitable surrogate for TMTA, while delayed word recall and ideational praxis were surrogates for TMTB ($r=0.5$, 0.6 , and 0.6 respectively). The COWAT surrogates were orientation and word recognition ($r=0.5$ at 12 months). (delayed recall, ideational praxis, orientation, and word recognition).

The model fit change in PLS over time with estimates drawn at an HbA1C of 7.2. The estimates of standard deviation and effect size for the change from baseline were -1.73 and 2.9, respectively. Given a sample size of 43, a two-sided alpha of 0.05 would result in 47% power to detect a significant effect. If we observe the estimated effect size and sd at the given sample size in the present study (Part 1) we would expect to observe a p-value of 0.059 indicating that the composite is somewhat more sensitive to treatment effects than the ADAS-cog 11.

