* ADAS-Cog will also be run using LZCF. If neither of these are significant, the cognitive composites and global statistical test (GST) will be assessed for significance to demonstrate proof of concept. It is acknowledged that the present study is underpowered to replicate the clinically meaningful effect size observed in the STEADFAST combined A- and B-study diabetes subgroup. Therefore, if the observed effect size (treatment difference) or percent slowing (treatment difference divided by the placebo change) is equal to or greater than the corresponding values from the STEADFAST pooled analysis (-0.92; -61%), this will be considered proof of concept. Lack of strict statistical significance is expected with this range of effect size due to the small n, but this result, in the context of the consistency of the effect seen in STEADFAST Part A with the STEADFAST Part B data would provide proof of concept for this compound.

§ All secondary variables will also be run using LZCF.

3 Estimand Specification

This SAP is constructed to conform to regulatory guidance. In particular, this section is included as recommended by ICH E9 (R1) Addendum on estimands and sensitivity analysis in clinical trials to the guideline on statistical principles for clinical trials (30 August 2017).

In accordance with ICH E9 Addendum, the specification of the estimand is included in this SAP with the 4 attributes detailed in ICH E9 Addendum, Section A.3.1:

- A. The Population, that is, the subjects targeted by the scientific question:
For this study, the population consists of subjects with AD and HbA1c of 6.5% - 9.5% who meet eligibility requirements for the study, receive double-blind medication, and have at least one valid post-baseline measure of ADAS-cog(14).
- B. The variable (or endpoint) to be obtained for each patient, that is required to address the scientific question:
For this study, the primary endpoint is Change in ADAS-cog(14).
- C. The specification of how to account for intercurrent events to reflect the scientific question of interest:
Due to the small sample size intercurrent events will not be accounted for in this analysis.
- D. The population-level summary for the variable that provides, as required, a basis for a comparison between treatment conditions:
For this study, the population-level summary for the variable is the least-squares mean (LSM) of the treatment difference in mean change from baseline in ADAS-cog(14).

4 Populations of Analysis

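### The SAP's proof-of-concept threshold (-0.92; -61%) names no scale, conflicts with the SAP's own pooled ADAS-cog estimate of -1.54, and otherwise appears only on a composite line with swapped labels

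*SAP*

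**What the plan says.** The footnote in SAP Section 2 is marked on H01 and H11, the ADAS-cog14 hypotheses, and opens with ADAS-Cog. It then turns to the composites and the global statistical test. It concedes that the study is underpowered to replicate "the clinically meaningful effect size observed in the STEADFAST combined A- and B-study diabetes subgroup". It then sets a route to proof of concept that needs no significance: the observed treatment difference, or the percent slowing (difference divided by placebo change), "is equal to or greater than the corresponding values from the STEADFAST pooled analysis (-0.92; -61%), this will be considered proof of concept".

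Figures elsewhere that could be the source:

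- SAP 1.6, ADAS-Cog: "The estimates of standard deviation and effect size for the change from baseline in ADAS-Cog was 3.4 and -1.54 respectively". This comes from the combined A- and B-study data read at HbA1c 7.2, and "The model utilized all individuals in the study". Stated power is 30%, expected p 0.144.
- SAP 1.6, Cognitive Composite: "The estimates of standard deviation and effect size for the change from baseline were -0.92 and 1.5, respectively". Then: "Given a sample size of 43, an alpha of 0.05 would result in 49% power to detect a significant effect". Expected p is 0.052.
- SAP 1.6, Modified Cognitive Composite: -1.73 and 2.9 in the same order, with 47% power and p 0.059.
- Protocol 1.1.3, diabetic subgroup: in the A-Study the azeliragon group "demonstrated a 3.8-point benefit on ADAS-cog relative to the placebo group (n=7) at Month 6"; in the B-Study it "demonstrated a 1.9-point benefit on ADAS-cog relative to the placebo group (n=13) at Month 6".

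**The concern.** A pre-specified success criterion should state the endpoint to which its number belongs. The footnote's mark points to ADAS-cog14, but the SAP's pooled ADAS-cog effect is -1.54. The only other -0.92 sits on the composite line, and there it is called a standard deviation. The population is also unclear: the footnote speaks of the diabetes subgroup, whereas the SAP 1.6 ADAS-cog model used everyone.

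The SAP expects 30% power on ADAS-cog and says it does not expect strict significance, so this rule may well decide whether Part 1 is called proof of concept. Part 1 in turn informs the endpoint, sample size, duration, eligibility and dose of Part 2 (Protocol 9.1). If the scale is left open, it could be settled after the data are seen.

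**Working it through.** **Inputs.** n = 43 and 1:1 allocation (SAP 1.4), taken as 21 and 22. SDs: 3.4 (ADAS-cog, SAP 1.6), 4 (ADAS-cog14 planning value, SAP 1.6 and Protocol 9.2), 1.5 (composite, labels corrected). SE = SD × √(1/21 + 1/22).

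**Step 1: reproduce SAP 1.6** (two-sample t-test, two-sided 0.05, 41 df).

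| Endpoint | Effect, SD used | Power, p obtained | SAP states |
|---|---|---|---|
| ADAS-cog as printed | 1.54, 3.4 | 30.5%, 0.145 | 30%, 0.144 |
| Composite as printed | 1.5, 0.92 | 99.9%, <0.001 | 49%, 0.052 |
| Composite, labels swapped back | 0.92, 1.5 | 50%, 0.051 | 49%, 0.052 |
| Modified composite as printed | 2.9, 1.73 | >99.9%, <0.001 | 47%, 0.059 |
| Modified composite, labels swapped back | 1.73, 2.9 | 48%, 0.057 | 47%, 0.059 |

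The ADAS-cog labels are right and both composite lines are swapped. An ADAS-cog effect of 0.92 with SD 3.4 would give 14% power and p 0.38, so it is not the value behind the SAP's ADAS-cog calculation.

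**Step 2: the 61%.** 0.92/1.5 = 0.613, which is the composite's effect over its SD. By the footnote's definition, 61% would need a placebo change of 0.92/0.61 = 1.51. No pooled placebo change is printed, so 61% cannot be verified.

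**Step 3: difference leg, true effect 0.** P(pass) = Φ(threshold/SE).

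- ADAS-cog, SD 3.4, SE 1.037: Φ(-0.92/1.037) = 18.8%; Φ(-1.54/1.037) = 6.9%.
- ADAS-cog, SD 4, SE 1.220: 22.5% at -0.92; 10.3% at -1.54.
- Composite, SD 1.5, SE 0.458: Φ(-0.92/0.458) = 2.2%.

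In SD units on ADAS-cog, -0.92 is 0.92/3.4 = 0.27, against 1.54/3.4 = 0.45 for the SAP's estimate.

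**Step 4: the full rule.** The legs are joined by *or*, so Step 3 gives lower bounds. Simulation with no true effect, counting slowing only when placebo declines, gives these pass rates. The placebo change is an assumption, shown as a range.

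| Assumed placebo change | ADAS-cog, SD 3.4 | ADAS-cog, SD 4 | Composite, SD 1.5 |
|---|---|---|---|
| 1.5 | 20% | 24% | 2% |
| 1.0 | 25% | 28% | 4.5% |
| 0.5 | 31% | 33% | 19% |

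**Step 5: composite standardised by visit.** SAP 1.6 standardises items by the baseline mean and SD; SAP 5.1.5.7 uses the mean and SD of each visit. Under the latter, the all-subject mean is zero at every visit, so the pooled mean change is about zero. Let a and p be the mean changes on active and placebo, with higher taken as worse. Then 21a + 22p = 0, so a − p = −(43/21)p = −2.05p. Slowing is then about −205% whenever placebo worsens at all. With no true effect that happens half the time, so the rule passes an inert drug about 50% of the time.

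**The case against.** The footnote also discusses the composites and the global statistical test before giving its benchmark, the note in SAP 5.1.4 concerns them too, and Figure 1 may name the scale. That stands: the intended scale is ambiguous, and this point does not assert that ADAS-cog was meant. Naming the composite in a figure would still leave the swapped labels, the unverified 61% and the two standardisations.

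Part 1 is a learning stage, the footnote is open about low power, and SAP Section 2 already allows proof of concept through significance on any listed outcome. That also stands, and limits the point to a decision threshold outside the alpha-controlled test. A stated success criterion still needs an endpoint.

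A reader might infer from the Protocol's 3.8 and 1.9 that -0.92 cannot be an ADAS-cog value, because any positively weighted average of those two is at least 1.9. The documents do not support this. The SAP's own -1.54 also lies outside that range, and a model on all subjects read at one HbA1c value need not be an average of two small subgroup differences. They are context to reconcile.

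**Conclusion.** The threshold is wrong as written. It has no stated endpoint, it conflicts with the SAP's only pooled ADAS-cog estimate, and its only matching source line is mislabelled. On ADAS-cog an inert drug meets -0.92 19% to 23% of the time on the difference leg, against 7% to 10% at -1.54. The full rule gives about 20% to 33% on ADAS-cog and 2% to 19% on the composite at placebo changes of 0.5 to 1.5, and about 50% on the composite if standardised by visit.

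Two stronger readings are not supported. One is that the rule is a one-in-five bar on ADAS-cog but a one-in-fifty bar on the composite. The 2% is the difference leg alone, so moving the rule to the composite does not by itself make it strict. The other is that -0.92 was certainly carried over from the composite. The match with 0.92/1.5 suggests this but does not prove it.

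The figures assume all 43 subjects are evaluable and an unadjusted comparison; the planned risk-adjusted model could differ. With 35 evaluable (the 18% planning dropout), the difference-leg rates become 21% to 25% on ADAS-cog and 3.5% on the composite. The SD of 3.4 comes from ADAS-cog11. The primary test's alpha is not affected.

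**What to change.** Before unblinding:

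1. Check the STEADFAST output and state the endpoint, population and source of -0.92 and -61%. If ADAS-cog is meant, use the verified ADAS-cog benchmark and reconcile it with -1.54.
2. Correct the swapped SD and effect labels for both composites in SAP 1.6.
3. Confirm that 61% is that endpoint's treatment difference over its placebo change, and print both figures.
4. If the composite is meant, first reconcile the standardisation in SAP 1.6 with that in SAP 5.1.5.7, because percent slowing has no useful meaning under visit standardisation.
5. Report the full *or* rule's pass rate under no effect.

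The cost is one check of existing output plus SAP wording. The downside is that a larger verified ADAS-cog benchmark is harder to meet. If it were -1.54 and that were also the true effect (SD 3.4), the difference leg would pass about 50% of the time, against Φ((1.54 − 0.92)/1.037) = 72% at -0.92.

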5.1 Efficacy Variables

Efficacy evaluation will include the primary endpoint (ADAS-cog14 for Part 1), secondary measures, and other efficacy markers.

Statistical analysis will be done on each primary and secondary variable independently.

5.1.1 Primary Efficacy Variable

The primary analysis will include assessment of the following variables.

- Mean change from Baseline to Month 6 in ADAS-cog14*

5.1.2 Secondary Variables of Analysis

- Mean change from baseline in the Amsterdam-IADL at Month 6.
- Mean change from baseline in CDR-sb at Month 6.
- Mean change from baseline in the FAQ at Month 6.
- Mean change from baseline in the MMSE at Month 6.
- Mean change of treatment on biomarkers and markers of inflammation

5.1.3 Exploratory Variable

- Mean change from baseline in ADAS-cog11 at Month 6.

5.1.4 Proof of Concept

- Mean change from baseline in Cognitive Composite at Month 6
- Mean change from baseline in Modified Cognitive Composite at Month 6
- Mean change from baseline in GST at Month 6

*If the ADAS-Cog is not significant ($P > 0.05$) the cognitive composites and global statistical test (GST) will be assessed for significance to demonstrate proof of concept. No correction will be performed for these comparisons since they are all testing the overall effect of treatment on progression of disease and are expected to be highly correlated.

5.1.5 Efficacy Scales

Generation of instrument total scores will be calculated from individual items. The following instruments that are used in this study are subject to statistical analysis:

5.1.5.1 Alzheimer's Disease Assessment Scale - Cognitive Subscale 90 point (ADAS-cog):

- Range: The scale range is 0 to 90 with higher scores indicating greater cognitive impairment.
- Brief description: The 14-Item Alzheimer's Disease Assessment Scale - Cognitive Subscale (ADAS-cog14) is a structured scale (approximately 45 minutes to complete) that evaluates memory, orientation, attention, reasoning, language, constructional praxis, delayed recall, digit cancellation, and maze-completion. The ADAS-cog14 scoring range is from 0 to 90, with higher scores indicating greater cognitive impairment (Mohs et al. 1997). The ADAS-Cog should always be administered prior to other cognitive measures. The ADAS-Cog will be administered at Screening, Baseline, Months 3 and 6 or in the event of early termination. Participants must have scores of ≥ 10 at Screening and Baseline to be eligible for participation in the study.

5.1.5.2 Mini Mental State Examination (MMSE):

- Range: The scale range is 0 to 30 with lower scores indicating greater cognitive impairment.
- Brief description: The MMSE is a brief 30-point test that is used to assess cognition (Folstein, 1975). It is commonly used to screen for dementia. In the time span of about 10 minutes, it samples various functions, including arithmetic, memory and orientation. The MMSE will be administered at Screening, Baseline, Months 3 and 6 or in the event of early termination. Participants must have scores of 21-26 at Screening and 19-27 at Baseline to be eligible for participation in the study.

5.1.5.3 Functional Activities Questionnaire (FAQ):

- Range: The score ranges from 0 to 30. Higher scores are associated with greater impairment.
- Brief description: The FAQ is an inventory of instrumental activities of daily living developed by (Pfeffer 1982). The FAQ is administered by asking the informant to rate patient's ability (0-3) on 10 different activities of daily living. The FAQ will be administered at Screening, Baseline, Months 3 and 6 or in the event of early termination.

5.1.5.4 Amsterdam-Instrumental Activities of Daily Living Questionnaire (A-IADL):

- Range: scoring range from 20 to 80, with lower scores indicating greater impairment.
- Brief description: The A-IADL is an adaptive questionnaire designed to assess impairments in instrumental activities of daily living in early dementia.(Sikkes 2013) The questionnaire is completed by a caregiver / informant. The original questionnaire consists of 70 items in seven categories and the administration time is approximately 20-25

minutes. The A-IADL total score is calculated using an item response theory method of scoring (Embretson and Reise 2000, Reise and Waller). Higher scores indicate greater functional impairment. The A-IADL will be administered at Screening, Baseline, Months 3 and 6 or in the event of early termination.

5.1.5.5 Clinical Dementia Rating Scale (CDR):

- Global CDR Range:
 - 0 = normal; healthy individuals
 - 0.5 = questionable dementia
 - 1 = mild dementia
 - 2 = moderate dementia
 - 3 = severe dementia.

- CDR sum-of-boxes (CDR-sb) range:

CDR-sb scores range from 0 to 18 with higher scores indicating greater cognitive impairment.

- Brief description: The CDR scale is used as a global measure of dementia and is completed by a clinician in the setting of detailed knowledge of the individual patient collected from interviews with the patient and caregiver (Berg, 1988). The CDR describes 5 degrees of impairment in performance on each of 6 categories including memory, orientation, judgment and problem solving, community affairs, home and hobbies, and personal care. Much of the information will therefore already have been gathered, either as part of normal clinical practice or as part of a research study. The interview takes approximately 40 minutes to administer.

The scores for each category can also be summed and this is known as the sum of box score (CSR-SB). The CDR will be conducted at Baseline and at Months 3 and 6 or in the event of early termination. To avoid patient fatigue, the CDR may be performed on a separate, but proximate, visit day than the other cognitive tests.

5.1.5.6 Global Statistical Test (GST):

A GST allows assessment of a global change in disease status/trajectory by standardizing and then combining measures. The GST will be a combination of 3 z-scores (ADAS-COG, CDR-SB, and A-IADL) with standardization calculated using the baseline mean and standard deviation for each score. The GST will be calculated for each subject at each timepoint by averaging the three z-scores and this GST will then be analyzed as a new outcome by calculating change from baseline to each visit.

5.1.5.7 Cognitive Composite:

Composites allow the global assessment of multiple aspects of disease as well as exclusion of items that do not contribute to progression and thus add noise to the data. The cognitive composite is composed of the ADAS-Cog comprehension, word finding

difficulty, and remembering test instructions variables. The composite will be calculated at each timepoint by summing the within visit z-scores for each item across individuals. Z-scores are calculated by subtracting the individual item score at visit x from the mean item score at visit x and dividing this value by the item standard deviation at visit x.

5.1.5.8 Modified Cognitive Composite:

The modified composite incorporates the cognitive composite variables as well as aspects associated with cognitive decline due to aging, specifically trail making test (TMT A/B) and Controlled Oral Word Association Test (COWAT). As these variables are not available in ELEVAGE; historic data (ADNI) was used to identify the best surrogate for each. All surrogates were found to be within ADAS-Cog individual items. Word finding difficulty was found to be a suitable surrogate for TMTA, while delayed word recall and ideational praxis were surrogates for TMTB ($r=0.5$, 0.6 , and 0.6 respectively). The COWAT surrogates were orientation and word recognition ($r=0.5$ at 12 months).

5.1.5.9 Biomarker:

Blood for plasma biomarkers will be collected at baseline as well as months 3, 6, and follow-up.

